4.1 VARIABLES/INTERVENTION

4.2 Variables

Table 2: Variables and Measures

	Method of Measurement	Number of items	Timeline
Social Capital (Primary Outcome)	Modified Social Capital Scale (based on Chen, et al.) ¹⁶	10	Phase I: Analysis of previously collected data Phase III: RCT participants at 0, 1, 4 and 10 months

	Qualitative Interviews	n/a	Phase I: In-depth interviews with YBMSM living with HIV Phase III: Pre- and post-intervention interviews
Engagement in HIV Care (Secondary Outcomes)			
Viral load suppression	Electronic medical record abstraction	n/a	Phase III: RCT participants at baseline, post-intervention and 10 months (if available; see page 17 for more detail)
Retention in Care	Electronic medical record abstraction	n/a	Phase III: RCT participants at 0 and 10 months
Antiretroviral adherence	Single item self-report ⁵²	1	Phase III: RCT participants at 0 and 10 months
Correlates (measuring other factors shown to relate to engagement in care among YBMSM in prior work)			
CD4 count (recent and nadir)	Electronic medical record abstraction	n/a	Phase III: RCT participants at baseline and post-intervention 10 months (if available; see page 17 for more detail)
Demographics	Survey questions	23	Phase III: RCT participants at 0, 1, 4 and 10 months
Depression	CES-D ⁵³	20	Phase III: RCT participants at 0, 1, 4 and 10 months
HIV Stigma	HIV Stigma Scale ⁵⁴	10	Phase III: RCT participants at 0, 1, 4 and 10 months
Ethnic Identity	Multi-Ethnic Identity Measure ⁵⁵	12	Phase III: RCT participants at 0, 1, 4 and 10 months

Gay Identity	Internalized Homonegativity Inventory ⁵⁶	23	Phase III: RCT participants at 0, 1, 4 and 10 months
Drug Abuse	CAGE-AID ⁵⁷	4	Phase III: RCT participants at 0, 1, 4 and 10 months
Social Support	Zimet's Multidimensional Social Support Scale ⁵⁸	12	Phase III: RCT participants at 0, 4 and 10 months
Group Dynamics	Selected items from Schulz, Israel and Lantz ⁵⁹	20	Phase III: RCT participants at 0, 1, 4 and 10 months
Social Networks	Lubben Social Network Scale	6	Phase III: RCT participants at 0, 4 and 10 months
Engagement with Health Care Provider	HCP Scale	13	Phase III: RCT participants at 0, 4 and 10 months
Identification and Involvement With the Gay Community	Identification and Involvement With the Gay Community Scale	8	Phase III: RCT participants at 0, 1, 4 and 10 months
General Wellbeing	The General Well-Being Schedule (GWB)	18	Phase III: RCT participants at 0, 1, 4 and 10 months
Psychological Distress	Brief Symptom Inventory	53	Phase III: RCT participants at 0, 4 and 10 months

Outcome Measures: The primary outcome measure will be social capital. The core measure of social capital that we will use is our Modified Social Capital Scale (MSCS) described above, which we developed and validated exclusively with YBMSM. Our aim is to discover whether social capital improves as a result of being in the social capital intervention, and also to see if there is any similar effect in the control arm. Secondary outcomes will be measures of HIV care engagement, namely: (1) Retention in care, (2) Adherence to medications, and (3) HIV viral load suppression. As per Institute of Medicine (IOM) recommendations, **retention in care** will be measured by determining, within the 10 months of the study period, (a) participation in continuous care, that is, at least two or more routine HIV visits at least three months apart, (b) receiving two or more CD4 tests, and (c) receiving two or more viral load tests.⁶⁰ **Adherence to antiretroviral medications** will be measured using a composite of single item self-report question and pharmacy refill records. **HIV viral suppression** will be considered achieved if the medical records report a viral load below the level of detection for the site-specific assay. Viral load values and appointment attendance will be extracted from the participants' EMR.

4.3 Intervention Content: As the details of the intervention will be influenced greatly by the formative research and the input of the YCAB, it cannot be described in full detail at this time. The main intervention delivery will consist of either a one day or a consecutive two day group

meeting among the YBMSM with time divided between health education and community photovoice project planning. Each group will contain ten YBMSM; we plan for six groups each in the control and intervention arms. As detailed above, the intervention will consist of a group-based curriculum in program planning and HIV education, culminating in the planning and implementation of a community photovoice project.

4.4 Outcomes: The primary outcome of interest for the RCT will be social capital, as we are aiming to determine whether or not our intervention is effective in increasing social capital. We will also look at engagement outcomes, to determine whether or not increasing social capital has an impact on care engagement in our participants.

4.5 Training for all study personnel: [name], her mentors and collaborators all have up to date training in research ethics that they will maintain throughout the duration of the study. The graduate research assistants, coordinators and public health program associate will also receive specific training related to their assigned tasks, including but not limited to qualitative interviewing, Research Electronic Data Capture (Redcap) survey administration, and qualitative coding and analysis. They will also, importantly, be trained in the process of obtaining informed consent. [name] and the other co-investigators have experience training and supervising staff and research assistants in all of these skills. Where possible, we will hire staff and research assistants with prior experience and/or coursework that is pertinent to this work.

4.6 Procedures for implementing and documenting informed consent: As noted above, we have requested a waiver of written consent for participation in the formative Phase I research including in-depth interviews with young Black MSM, and in-depth interviews with key informants in the community. Verbal consent scripts are included in Appendix A. Written consent will be obtained for participants in the Phase III RCT.

4.7 Plan for monitoring the informed consent/assent/permission process: All study staff who have direct contact with participants will be trained in the process of both verbal and written consent administration by [name]. This training will include instruction on the importance and critical elements of informed consent, as well as role-playing to demonstrate proper and improper consenting techniques. New research assistants will be supervised for at least the first three consents that they do in order to observe and provide feedback; once the trainer has determined that they are able to conduct the discussion independently, they will no longer be supervised.

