Retention Plan: Our previous experiences have demonstrated the need to pay careful attention to participant retention: part of the role of the study staff is to remind participants about intervention sessions and study visits, scheduling, and discussing any issues they face in the trial procedures. In [name] ongoing work with the Metropolitan Atlanta Community Adolescent Rapid Testing Initiative (MACARTI) trial, these procedures have resulted in at least an 87% retention among participants who were primarily HIV-positive YBMSM (and may be higher as the follow-up period has not yet ended).

Clinical Outcome Measures: Viral load values and appointment attendance will be extracted from the participants' electronic medical records (EMR). The goal is to abstract measures that correspond to the 0 month (baseline) and 10 month (long term follow-up) time points at which participants will be completing surveys. However, we recognize that lab tests (CD4, VL) in the clinical setting may not necessarily be conducted at a time that corresponds to the survey time point. In light of this limitation, and to make the procedures more uniform, we plan the following: (1) the baseline viral load will be the most recent measurement preceding study participation. If this is >6 months prior to the date of enrollment, this will be considered a missing value. (2) The 10 month viral load will be the first value drawn on or after the date that is exactly one year from the beginning of study participation. If this test is done >6 months after the target date, it will be treated as a missing value.

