5.1 DATA ANALYSIS AND MANAGEMENT

5.2 Data Analysis: We will be collecting both qualitative and quantitative data during the course of this survey.

5.2.1 Quantitative analyses: Will be conducted using SAS or SPSS statistical software. An odds ratio plus the 95% confidence interval will be calculated to measure the degree of association between retention in care measures and total social capital (all analyses will also be computed for bonding/bridging subscales alone, as well as for item clusters focusing on different dimensions of social capital). Odds ratios will also be calculated to measure the degree of association between other risk factors (education, employment, age, depression, substance use, HIV stigma and CD4 cell count) and patient retention.

Additionally, total social capital will be compared between engaged and non-engaged patients using a two-sided two-sample t-test. Other potential risk factors will be compared between retained and non-retained patients using a chi-square test or Fisher's exact test for categorical covariates and a two-sided two sample t-test for continuous covariates.

Multivariable analyses: Covariates significant to at least $P \leq 0.20$ in the univariable analyses will be used in multivariable logistic regression analyses. Although empirical techniques will be used to identify important covariates, theoretical expectations from our social capital conceptual framework will also augment these decisions. Interactions between covariates will be evaluated, either because suspicions are raised by clinical judgment before the analyses are performed or by statistical examination. Forward stepwise selection will be used if necessary to choose prognostic variables for a multivariable logistic regression model. The odds ratio and its 95% confidence interval will be calculated for each risk factor in the presence of others in the final model.

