Phase 1- In-depth interviews with YBMSM and key informants: All interviews will take place in a private and quiet room within the IDP clinic or in the case of key informants, at the location of their choosing. [name] has extensive experience conducting such interviews in the clinic for prior research studies and has found this location to be acceptable and comfortable for participants. Interviews will be conducted by a graduate research assistant who will be trained in qualitative methods and interviewing techniques. All interviews will be digitally recorded for subsequent professional transcription. Written informed consent will be obtained before beginning the interview. Interviews will be expected to last approximately 60-90 minutes each. All digitally recorded data will be transcribed verbatim by a professional business transcription service. Qualitative data will be de-identified during this transcription process. Transcripts will then be uploaded into the

MaxQDa qualitative data management software (VERBI Software, Berlin, Germany) for further processing and analysis.

Phase 1- social capital surveys: this data was collected as part of our pilot work prior to the award period. It has already been de-identified and is ready for analysis.

Phase 2 and 3-EMR extraction: Viral load values and appointment attendance data will be extracted from the participants' electronic medical records (EMR) to determine retention and viral suppression outcomes. Clinical data will be entered directly into the Redcap database via a secure online form by graduate research assistants. This will be done at the baseline and 10 month time points.

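### Retention is counted over only 10 months, which would misclassify some men seen about every 6 months, and its planned month-0 value has no usable definition

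*Combined protocol and SAP*

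**What the plan says.** Section 4.2 (Outcome Measures) names retention in care as the first of three secondary outcomes. It is determined "within the 10 months of the study period, (a) participation in continuous care, that is, at least two or more routine HIV visits", and the sentence continues "at least three months apart, (b) receiving two or more CD4 tests, and (c) receiving two or more viral load tests". It does not say whether (a), (b) and (c) must all be met or are three separate measures. Section 5.2.1 refers to "the degree of association between retention in care measures and total social capital", in the plural, and also compares retained with non-retained patients.

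Table 2 schedules retention as "Phase III: RCT participants at 0 and 10 months". Section 5.2 (Data collection) says of chart extraction: "This will be done at the baseline and 10 month time points". No look-back period is given for retention at month 0.

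Section 2.3 (Clinical Outcome Measures) does give such a rule for viral load: "the baseline viral load will be the most recent measurement preceding study participation", treated as missing if more than 6 months before enrolment. The later value is set as follows: "The 10 month viral load will be the first value drawn on or after the date that is exactly one year from the beginning" of participation, and it is missing if drawn more than 6 months after the target date.

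No routine visit or laboratory interval is stated anywhere.

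**The concern.** Retention is read from ordinary clinic care, but the window is borrowed from the survey schedule. Two visits six months apart fit into 10 months only if the first comes early enough. A man who keeps every appointment can therefore be scored not retained because of where enrolment fell in his visit cycle.

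The month-0 problem is separate. A baseline value is planned, but a definition limited to the study period cannot produce one. Without it, men who became retained cannot be told from men who already were, and baseline retention cannot serve as a covariate.

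Retention serves Aim 3b and is the outcome in the odds-ratio models of section 5.2.1, so both points affect results the plan intends to report.

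**Working it through.** The plan gives no rate or power for retention, so there is no figure of its own to reproduce. The check uses the geometry of the window.

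**Inputs from the documents.** Window W = 10 months; two visits at least 3 months apart (section 4.2).

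**Assumptions.** Visit interval g is not in the documents, so a range is shown. Attendance is perfect, and the first visit falls at random between 0 and g months after enrolment.

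**Formula.** With the first visit at time U, the second is at U + g. Both fall in the window if U ≤ W − g. For g between 3 months and W, the share passing is min(1, (W − g)/g).

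**Visit criterion, exact intervals:**

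| Interval g | W = 10 months | W = 12 months |
|---|---|---|
| 3, 4 or 5 months | 100% | 100% |
| 6 months | (10 − 6)/6 = 67% | (12 − 6)/6 = 100% |
| 7 months | (10 − 7)/7 = 43% | (12 − 7)/7 = 71% |
| 8 months | (10 − 8)/8 = 25% | (12 − 8)/8 = 50% |

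**Irregular intervals, by simulation:**

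- About 4 months (SD 0.5): 99.5% pass in 10 months.
- About 5 months: 97% pass in 10 months if intervals vary evenly by ±0.5 month, and 96% with an SD of 0.5 month.
- About 6 months, ±1 month: 66% pass in 10 months and 94% in 12.
- About 6 months, SD 0.5 month: 67% and 97%.

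**Share of all fully attending men misclassified.** If a fraction s is seen every 6 months and the rest every 5 months or more often, the share is s/3: 8% for s = 25%, 17% for s = 50%, and 25% for s = 75%.

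**Effect on the comparison.** Illustration only: true retention 60% and 80%, 60 men per arm, everyone 6-monthly, two-sided 5% test, no allowance for group clustering, and no non-retained man scored as retained. Observed proportions become 60% × 2/3 = 40% and 80% × 2/3 = 53.3%.

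- Risk difference: 20 points falls to 13.3.
- Odds ratio: (0.8/0.2)/(0.6/0.4) = 2.67 falls to (0.533/0.467)/(0.4/0.6) = 1.71.
- Risk ratio: 1.33 both times.
- Power: 67% falls to 31%. This is the extreme case, and the loss shrinks as fewer men are 6-monthly.

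**Laboratory components.** If (b) is mandatory, 6-monthly CD4 testing gives the same 67%. Yearly testing gives 0% in 10 months, and the same formula gives 0% in 12. The missing combining rule therefore matters whatever the window.

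**Section 4.2 against section 2.3.** The baseline viral load precedes participation and the 10-month one is drawn at 12 months or later, so neither lies inside the 10-month retention window. A man tested shortly before enrolment and at months 6 and 12 has both suppression values, yet only one in-window test for criterion (c).

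**The case against.** The strongest reply is that the decisive input is an assumption. No visit interval is stated, and this population includes newly diagnosed and re-engaging men (section 5.9), who may be seen more often than 6-monthly. At 3 to 5 months the window does little or no harm. That stands, and it makes the size conditional.

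A reader might take the 6-month limits in section 2.3 as evidence that the plan expects 6-monthly care. They are cut-offs for calling a viral load missing and say nothing about visit frequency.

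A reader might also suppose that a man recruited at a clinic visit has almost no chance of two in-window visits. That needs a roughly 6-monthly schedule, enrolment just after a visit, and that visit not counted. Section 3.6 describes many recruitment routes, with on-site contact mainly for screening, and nothing excludes enrolment-day care.

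A window matching the 10-month follow-up is also a coherent choice, and the source cited for the definition cannot be consulted here. Randomisation keeps the comparison of arms at 10 months valid without a baseline value, and section 5.2.1 specifies no change-in-retention analysis. These points limit the consequence. They do not make the planned month-0 value computable.

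**Conclusion.** The point holds in a limited form. If some men are seen about every 6 months, about one third of those who miss nothing would fail the visit criterion in 10 months, against 0 to 6% in 12 months. This rests on perfect attendance, a random enrolment date and an assumed interval.

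If the misclassification is similar in both arms, it dilutes the risk difference and odds ratio and leaves the risk ratio unchanged. A reader might infer that the trial is biased, or that the rule penalises improvement. The first does not follow, and the second would need the intervention to change visit spacing, which the documents do not suggest.

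Three other strong readings also go too far:

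- Fully retained men do not fail as a class; two thirds pass even at 6 months.
- The text does not settle that all three components are required.
- A baseline is not absent from the plan; it is scheduled but undefined. That gap is separate from the window and does not cause the misclassification.

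For a secondary outcome with a cheap remedy, the change should be made.

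**What to change.** In section 4.2 and Table 2:

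- Measure retention over 12 months from enrolment, counting care received on the enrolment day.
- Apply the same definition to the 12 months before enrolment as the month-0 value, with a separate category for men diagnosed in that period, and use it as a covariate.
- State whether (a), (b) and (c) are all required or are reported separately.

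In section 5.2, change the chart-extraction timing to match. Word the month-10 record release to cover care through month 12 at any facility. The survey visits can stay at 10 months.

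The cost is wording and two more months of chart reading; no visit is added, and section 2.3 already needs charts at and after one year. The downsides are that the last participants' retention data close two months later, and that some care at a new facility after month 10 may be missed.

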Study visits: In addition to attending the intervention sessions, participants in both arms will be asked to come to the IDP clinic or Rollins School of Public Health to participate in three study visits: One at baseline before starting the intervention (0 months), immediately after completing the intervention (around 1 month), 4 months and a long term follow-up at 10 months after study completion. The main purpose of these visits will be to complete a survey to measure any change in social capital between the pre- and post-intervention periods. The survey (Appendix F) will also include measures of other theoretically relevant constructs including depressive symptomatology, stigma, and social support. We will also verify the participants' most recent medical care facility and obtain medical record release forms to facilitate abstraction of data on engagement outcomes. Participants will receive tokens of appreciation for each completed study visit (\$25 for the first visit and \$50 for the second) and given MARTA cards at these visits.

Follow-up qualitative interviews: We will conduct n=30 qualitative in-depth interviews in Year 4 with a subset of interested participants who were enrolled in the social capital intervention arm, in order to understand their experiences in the program and solicit feedback for future implementation of the intervention. Procedures and analytic plans will be as described in the Phase 1 interviews above. Participants will sign a separate informed consent to participate, and will receive an additional \$25 token of appreciation for their time if they choose to do so. The maximum total amount for tokens of appreciation for participants who do all sessions is \$175.

2.4 Audience and stakeholder participation: Our study follows a community-based participatory approach designed to ensure stakeholder participation. First, we will conduct interviews with community stakeholders to inform our understanding of social capital in our target population. Second, we will create a youth community advisory board (YCAB) designed specifically to engage members of the community at each step of the process. Finally, at the end of the project, we will plan to disseminate findings not only in academic publications but also in a community forum.

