Phase III Randomized Controlled Trial: Recruitment: We will recruit YBMSM from the IDP clinic as well as from our CBO partners AID Atlanta, NAESM and Positive Impact. Community recruitment will occur via self-referral from email and social media announcements as well as posted flyers at community locations and within the clinic. When interested individuals contact the study team, they will be screened for eligibility criteria via phone or online survey. Of note, participants do not need to be patients at the IDP clinic; as long as they consent to release of medical records and chart abstraction by our study team, we will be able to obtain HIV related outcome data. If eligible, study staff will then contact the participant to schedule an interview. We will also directly contact and offer screening to patients in our clinic who meet the age criteria (aged 18-29), as long as the medical providers agree to the patients being directly approached at that time. The eligibility screening can be done in person, via phone or via an online survey. At other times, we will also pass out flyers and other promotional materials at events that may be likely to be frequented by YBMSM (e.g., Gay Pride festival), and we will consult with our YCAB for advice about such venues and events. We will also do on-site recruitment at the clinic and community venues/events, in which we will approach potential participants and ask if they are interested in completing an online screening survey for eligibility in our study. If yes, they will have the option to complete the survey on a tablet at that time. We will also use the snowball sampling method to recruit participants. After completing the intervention, we will distribute 5 flyers to each participant to distribute to people within their social networks as referrals to our program. These flyers will be marked with a number that is unique to each participant. If a potential participant contacts us through the referral method, they will provide the number marked on the flyer. These potential participants will then complete an online screening survey for eligibility in our study.

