Phase 2 and 3-surveys: In addition to attending the intervention sessions, participants in both arms will be asked to come to the IDP clinic to participate in three study visits: One at baseline before starting the intervention (0 months), immediately after completing the intervention (around 1 month), 4 months, and a long term follow-up at 10 months after enrollment. The main purpose of these visits will be to complete a survey using the Research Electronic Data Capture (Redcap) online survey platform on an electronic tablet. The Redcap survey will contain our MSCS and will be used to measure change in social capital between the pre- and post-intervention periods. We will also verify the participants' most recent medical care facility (since the last visit) and obtain the participants' signatures on medical record release forms to facilitate abstraction of data on engagement outcomes.

5.3 Data Entry, Editing and Management:

All survey and clinical data will be entered into a password protected, HIPAA compliant RedCap database. The database will be accessible only to the study team. Any subsequent datasets that are exported for analysis will be stripped of identifying information and will only be linked by a participant ID number.

In terms of identifying discrepancies, some of this will be done prospectively by building quality checks into the Redcap data collection system—for example, if certain data do not line up between the baseline and follow up surveys (e.g. participant's date of birth), participants will be prompted to re-enter their answers to that question. Once per month, data will be reviewed in more detail for potential errors. We will ask our biostatistician to conduct descriptive analyses in order to help us identify outliers and return to the original data source as needed to confirm outlying values.

Qualitative interviews will be transcribed verbatim. Identifying information (names) will be taken out at the time of transcription. Files will be kept in a secured shared drive (Emory Box or equivalent) for access by study staff only.

5.4 Provisions for protecting privacy:

Breach of privacy is a concern in this study as identifying information/personal health information will be collected as part of the data collection process. Additionally, efforts to

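### Viral suppression is defined by each site's own assay limit, so if those limits differ the same viral load can be classified differently between facilities or between time points

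*Combined protocol and SAP*

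**What the plan says.** Section 4.2 (Outcome Measures) gives the role of the endpoint: "Secondary outcomes will be measures of HIV care engagement, namely: (1) Retention in care, (2) Adherence to medications, and (3) HIV viral load suppression". Suppression is achieved if the medical record reports a "viral load below the level of detection for the site-specific assay". The data source is routine care: "Viral load values and appointment attendance will be extracted from the participants' EMR". No central or study laboratory is described.

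Section 3.6 (Enrollment), on RCT recruitment, states that "participants do not need to be patients at the IDP clinic", provided they agree to the release of their records. Section 2.3 (Study visits) has staff verify the "most recent medical care facility and obtain medical record release forms", and section 5.2 (Data collection, surveys) makes clear that this covers the period since the previous visit. Section 5.9 holds further Atlanta clinical sites in reserve in case enrollment falls short, which it calls unlikely.

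Section 2.3 (Clinical Outcome Measures) sets rules to make the viral load data more uniform, but these cover timing only. Section 5.2.1 contains no adjustment for site or assay and no sensitivity analysis on the suppression definition.

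**The concern.** A detection limit is a property of the assay, not of the participant. Where one laboratory serves the whole trial, being below detection amounts to a fixed cut-off. Where several do, the cut-off moves with the laboratory. The protocol allows for several facilities and for moves between them, yet ties the outcome to whichever assay produced the result.

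Two things are at stake. Within a person, status could change between baseline and follow-up because of a change of clinic or assay, with no change in viral load. Across people, the suppression percentage would combine different thresholds, which makes it hard to compare with other reports and adds noise to the arm comparison. The problem is largely avoidable, because section 5.2 (EMR extraction) already plans that "Viral load values and appointment attendance data will be extracted", not just a suppressed/unsuppressed flag.

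**Working it through.** The documents state no sample size, power or expected rate for viral suppression in the trial, so there is no figure to reproduce. The check has two parts.

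**1. Does the rule allow the inconsistency?**

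- Threshold: site-specific, with no number (4.2).
- More than one facility: permitted (3.6).
- Change of facility: anticipated by the re-verification (2.3, 5.2).
- Time for a change: the baseline value may be up to 6 months before enrollment. The follow-up value is the first on or after one year from the start of participation and may be up to 6 months later (2.3). The two can therefore be about 6 + 12 + 6 = 24 months apart.
- Correction elsewhere: none (2.3 covers timing only; 5.2.1 is silent).

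Take two laboratories with reporting limits L1 < L2. A value v with L1 ≤ v < L2 is detectable at the first and below detection at the second. The rule classifies it both ways. This follows from the text if, and only if, the limits differ.

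**2. How large could it be?** All inputs here are assumptions, except 60 per arm (2.3) and 46% (1.2.4).

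*Gap between sites.* Let q be the share of viral loads lying between the two limits, and f the share of participants at the site with the higher limit. Identical patient groups would differ by q between the sites. The overall rate moves by q × f relative to using the lower limit throughout.

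- q = 2%, 5% or 10%: the sites differ by 2, 5 or 10 points.
- q = 2%, f = 10%: 0.02 × 0.10 = 0.2 points.
- q = 10%, f = 50%: 0.10 × 0.50 = 5 points.

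*Dilution of an arm difference.* Take a common cut-off as the reference. Let m be the share of people suppressed by that cut-off whom the site rule calls unsuppressed, equal in both arms. Then observed difference = (1 − m) × true difference. Here m is the share of those people with values between the limits, times the share tested at the more sensitive laboratories.

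- 0.05 × 0.5 = 2.5%: 20 points becomes 20 × 0.975 = 19.5.
- 0.20 × 0.5 = 10%: 20 points becomes 20 × 0.90 = 18.

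*Spurious arm difference.* This is q times the arm imbalance in f.

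- q = 5%, imbalance 10 points: 0.05 × 0.10 = 0.5 points.
- q = 10%, imbalance 20 points: 0.10 × 0.20 = 2 points.

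The chance imbalance in f has SD √(2f(1 − f)/60), ignoring group effects. That is 5.5 points at f = 10%, 8.4 at 30% and 9.1 at 50%. An imbalance of 10 to 20 points is thus roughly one to two SDs at f = 30% or 50%, and more extreme at 10%.

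*Scale.* Section 1.2.4 quotes 46% suppression for ages 13 to 24 at the IDP clinic within a year of starting therapy. This is a different population and is used only for illustration. The 95% half-width for an arm difference at 60 per arm is 1.96 × √(2 × 0.46 × 0.54/60) ≈ 0.178, about 18 points before attrition or clustering. The shifts in the arm comparison above, 0.5 to 2 points, are small against that.

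**The case against.** The strongest reply is that the premise is unproven. The documents give no assay limits, no number of contributing facilities and no rate of moving between them. If all contributing laboratories share one limit, the definition does no harm. This stands, and the point is conditional for that reason.

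A reader might infer that the outcome does mix thresholds across many clinics, or that the arm comparison is biased. The documents do not support either. Section 3.6 names one clinic and three community partners and merely permits care elsewhere; the extra sites in 5.9 are a contingency. Randomization spreads baseline care sites over the arms in expectation. The facility at follow-up is determined after randomization, so balance there is an assumption, but nothing in the documents suggests that the arms would move differently. Nor is suppression designated a key endpoint: it is listed third of three secondary outcomes, and section 3.5 powers the trial on social capital alone.

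It can also be said that being below detection is an explicit, reproducible definition suited to abstraction from records, and that calling the alternative correct is partly a choice. That is fair. The case for a common cut-off is comparability, not that the current rule is invalid.

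Finally, the change is not free of new data: assay limits are not among the items listed for extraction, the highest limit may not be known until records are complete, and one less sensitive laboratory could set the threshold for everyone. These costs are real but small, and the fix has to deal with them.

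**Conclusion.** The concern holds in conditional form. The rule in 4.2 can classify the same viral load differently by facility or by time point, and nothing elsewhere in the plan corrects this. Whether it will do so depends on differences in assay limits that the documents do not report, so the actual size is unknown.

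On the assumed ranges, the effect on the arm comparison is a loss of 0.5 to 2 points from a 20-point difference, or a spurious difference of similar size under an unlucky imbalance. It is mainly non-differential dilution and modest beside the sampling error. The reported percentage is more exposed, moving by 0.2 to 5 points. The primary outcome is unaffected. The change is worth making because it is cheap and because the cut-off is credible only if fixed before results by arm are seen.

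**What to change.** In 4.2, classify suppression from the abstracted viral load value with one common copies/mL cut-off for all laboratories and all viral load time points: baseline, any post-intervention value (Table 2 lists one) and 10 months.

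- Set the cut-off no lower than the highest reporting limit among contributing laboratories. Below that, a laboratory with a higher limit could not say on which side a result falls.
- Record each result's reporting limit at abstraction.
- Fix the cut-off blind to arm, once the contributing laboratories' limits are known and before any outcome is tabulated by arm.
- Count results reported as not detected or below the limit as suppressed.
- Keep the site-specific definition as a sensitivity analysis. This also shows whether one less sensitive laboratory has driven the choice of cut-off.

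The cost is a short change of wording, one extra abstraction field and a slightly less strict definition at laboratories with more sensitive assays. The change concerns outcome classification only and has no bearing on clinical care.
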